One patient in cohort 8 (600mg) experienced one dose limiting toxicity (DLT). This was an elevation of the gamma-glutamyl transferase (GGT), grade 3, that was asymptomatic and deemed not clinically significant by the investigator. There has been one unrelated SAE with fatal outcome due to respiratory tract infection in cohort 1 (15 mg). No deaths due to drug-related AEs have been reported to date.

CB-103 is rapidly absorbed after oral administration and reaches Cmax within 1 to 2 hours of dosing. Plasma exposure increases with increasing doses. There were no signs of saturated absorption in the dose range tested. The elimination half-life is approximately 20 hours and CB-103 accumulates about 2-fold with repeated daily administration. Steady state concentrations are reached within one week of dosing.

Hair follicles used as surrogate tissue were obtained at pre-defined time points to measure changes in NOTCH target genes expression by CB-103 treatment. In patients in the ongoing phase 1 study, average target gene downregulation on Cycle 2 day 1, 1h post-dose compared to baseline prior to treatment with CB-103 showed a strong dose-dependent down-regulation of several NOTCH target genes, reaching values higher than 70% inhibition at the highest CB-103 dose tested in this series (250mg). Additionally, a sustained time-dependent down-regulation of NOTCH target genes was observed, reaching up to a 90% inhibition after 4 weeks of daily administration of CB-103 at 250mg dose.

Clinically, best response was durable stable disease (SD) with no or only mild AE at doses showing target engagement. Ten patients with ACC had radiologically confirmed SD, of whom 4 patients had a Notch activating mutation or fusion. The Notch status of the other patients is under investigation. Disease control rate (DCR) of 19 ACC patients at 3 months was 68% (DCR defined as number of patients with CR, PR, or SD divided by the number of patients treated).

Based on the safety profile, the Cohort Review Committee declared the dose of 600mg given once daily QD as a safe dose. The MTD was not reached. The Bayesian statistical model allows further dose escalation to 800mg. Because the visual symptoms caused considerable discomfort to some patients, the 600mg dose was declared as provisional RP2D for further exploration in the dose confirmatory cohort. In parallel, a twice daily schedule of CB-103 is being explored.

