#### **Part A – Dose escalation (Phase I)**

Part A will be a dose-finding study based on a 2-parameter BLRM to investigate the safety and tolerability of sequentially enrolled dose cohorts of at least 3, up to 6 patients per dose cohort. Depending on the BLRM, additional patients may be enrolled in some dose cohorts. The first two patients of each dose level will be enrolled in a staggered approach with at least 1 day apart between first dosing of these patients. Subsequent patients may be enrolled concurrently, with at least 1 day apart from the second patient, whereby a dose cohort must be completed with regards to the DLT assessment period and be reviewed by the Cohort Review Committee (CRC) established for this study before further patients are dosed in the next dose cohort. The BLRM will be assessed for those patients satisfying the requirements for inclusion in the dose-determining set (DDS). After completion of a given dose cohort, or at any time the BLRM is updated, the decision to dose escalate and the actual dose and schedule chosen will depend on the recommendation of the BLRM about the highest admissible dose according to the EWOC principle and medical review of available clinical, pharmacokinetic and laboratory data. The outcome of these analyses and the respective datasets will be reviewed by the CRC consisting of the Investigators, Sponsor and CRO representatives, and independent functional experts as required (see Section 5.1.4.1). The CRC will make the decision to determine the next dose level and schedule for the next dose cohort.

Any dose level cohort that has been declared safe after the DLT period, may be expanded by individual patients in order to collect additional pharmacodynamic (PD) and pharmacokinetic (PK) information to support and/or confirm the mechanism of action and

explore doses at the currently tolerated dose level or below. These patients will be counted for the respective cohort at the future CRC meetings and will contribute towards the overall safety, PK, PD and clinical efficacy evaluation.

When the MTD/RP2D is defined, based on the decision of the CRC, approximately 45 additional NOTCH-positive patients with recurrent/metastatic ACC, breast cancer, r/r T-ALL/T-LBL, or any other solid tumour with proven Notch pathway activation will receive the MTD/RP2D dose to ascertain that optimal safety related to efficacy and pharmacodynamics in the tumour and in peripheral blood are achieved.

[figure not shown]

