##### **Estimation of MTD / RP2D**

A two-parameter BLRM employing the EWOC principle will be used during the escalation phase for selection of doses to investigate and for estimation of the MTD. The general plan is that cohorts of patients will receive escalating doses of CB-103 until the MTD is reached. Each cohort will consist of newly enrolled patients.

Estimation of the MTD during the escalation phase of the study will be based upon the estimation of the probability of DLT in cycle 1 in patients in the DDS. If MTD cannot be reached in the dose escalation part, the RP2D will be determined based on the review of DLTs, adverse events/serious adverse events, laboratory, PK and PD data and selected as the dose resulting in the best therapeutic window for CB-103.

At all decision time points, the adaptive BLRM permits alterations in the dose increments based on the observed toxicities. It will be possible for some dose levels to be skipped or additional, intermediate dose levels or dosing schedules to be added during the course of the study.

Dose escalation will in general not exceed a 100% increase from the current dose being studied with the exemption of the dose escalation following the starting dose of 15 mg CB-103 where the next dose of CB-103 in the next dose level might be adapted if the exposure of CB-103 (AUC0-24) is much lower than the expected value of approximately 600 µg\*h/mL which was determined to be safe from the non-clinical GLP safety and toxicology studies in rats and dogs. If clinically relevant toxicity CTCAE ≥ grade 2 is observed and suspected to be related to CB-103 in > 1 patient within the current cohort, the escalation to the next cohort will be restricted to ≤ 50% of the current dose. Cohorts may be expanded at any dose level below the highest dose deemed unacceptable in order to better understand safety, tolerability, PK or PD.

Dose decisions during escalation are however not limited to the provisional dose levels provided in Table 3. Based on the recommendation of the BLRM regarding the highest

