dose that may not be exceeded at any decision point during escalation and the maximum increase in dose allowed by the protocol, intermediate doses may be administered to subsequent new cohorts of patients. This includes doses lower than the starting dose or an intermediate dose between the current and next (lower or higher) provisional dose and different schedules. To further characterise the safety (e.g. specific suspected treatment-related adverse events) or PK/PD of CB-103 a dose that is considered acceptably safe, i.e., shown to be lower than any potential MTD, may be expanded.

Dose escalation may be terminated at any time based on emerging safety concerns without establishing the MTD.

The DLT period starts from the administration of the first oral dose until 28 days after the first oral dosing (1st cycle of CB-103). Intermediate dose levels of CB-103 may be explored, e.g. in case of MTD.

During the MTD/RP2D confirmatory cohort, if in specific subgroups (e.g., by indication or ethnicity) a higher rate of toxicities occurs or the PK profile of CB-103 is different, dose adjustments in such subgroups may be decided.

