#### **10.5.1.2 Dose-Finding of Single Agent CB-103**

A 2-parameter BLRM (Neuenschwander et al., 2008) will be used for dose escalation. Standardised doses will be used such that one of the doses ( $d^*$ ) equals 1, e.g., doses are rescaled as  $d/d^*$ . As a consequence,  $\alpha$  is equal to the odds of the probability of toxicity at  $d^*$ . All information currently available about the dose-DLT relationship of CB-103 is summarised in a prior distribution. For this study, this includes pre-clinical data about the starting dose and predicted MTD of CB-103 within different animal species. This prior distribution is then updated after each cohort of patients with all of the DLT data available in the DDS from the current trial. Once updated, the distribution summarises the probability that the true rate of DLT for each dose lies in the following categories:

- [0,16%) under-dosing
- [16%,33%) targeted toxicity
- [33%,100%] excessive toxicity

The EWOC principle (Babb et al., 1998, Neuenschwander et al., 2008) mandates that any dose of CB-103 that has more than a 25% chance of being in the excessive toxicity category is not considered for the next dose cohort. After a clinical synthesis of the available toxicity information (including adverse events that are not DLTs), PK, PD, and efficacy information as well as the recommendations from the Bayesian model, the CRC will determine the dose regimen for the next cohort at a dose-escalation teleconference. In case that another regimen is evaluated during the study, a separate 2-parameter logistic regression will be used for the assessment of the respective DLT rates. However, all data that are available from the other regimen (or regimens) before "First Patient First Visit" (FPFV) for the new regimen has happened will be incorporated into an informative, meta-analytic predictive (Neuenschwander et al 2015) prior distribution. This prior distribution will be mixed with a weakly informative prior distribution to hedge against a potential prior-data conflict.

The frequency of DLTs will be tabulated by dose for patients in the dose escalation phase and information about the DLTs will be listed by dose.

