### Hypothetical data scenarios

Hypothetical data scenarios are shown in Table 1. These scenarios reflect potential on-study data constellations and related escalation as allowed by the model and the 100% escalation limit. For each scenario, the probability of overdose for the current dose, as well as the next potential dose and related probabilities of under-dosing, target dose and over-dosing are shown.

For example, scenario 1 represents the case that no DLT is observed in three patients at the starting dose of 15 mg. In this case, the next dose permitted by the model and by the 100% escalation rule is 30 mg. Similarly, scenario 2 represents the case that one DLT is observed in the first cohort of three patients at 15 mg, the model would than not allow to escalate to 30 mg and would require more patients enrolled on the dose level of 15 mg. Scenario 6 represents the case that two DLTs are observed in the second cohort in three patients at 30 mg. The model then allows a de-escalation to 15 mg. Despite the fact that no DLTs were seen in the previous cohort (6 patients in total), the model reacts immediately to the data observed at 30 mg and requires a de-escalation to 15 mg. This case illustrates the adaptive behaviour of the model even in extreme situations.

**Table 1** Hypothetical data scenarios

Scenario	Dose	#DLT	#Pat	Current Dose - P(OD)	Next Dose	Next Dose - P(UD)	Next Dose - P(TD)	Next Dose - P(OD)
1	15	0	3	0.011	30	0.89	0.079	0.031
2	15	1	3	0.239	15	0.467	0.294	0.239
3	15	2	3	0.685				
4	15	0	3					
	30	0	3	0.007	60	0.871	0.094	0.035
5	15	0	3					
	30	1	3	0.121	30	0.602	0.277	0.121
6	15	0	3					
	30	2	3	0.4	15	0.439	0.356	0.206
7	15	0	3					
	30	1	6	0.034	60	0.53	0.308	0.162
8	15	0	3					
	30	0	3					
	60	1	3	0.102	60	0.61	0.289	0.102

CONFIDENTIAL

May not be used, divulged, published, or otherwise disclosed without the consent of Cellestia Biotech AG

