#### Part A – Dose escalation (Phase I)

Part A will be a dose-finding study based on a 2-parameter BLRM to investigate the safety and tolerability of sequentially enrolled dose cohorts of at least 3, up to 6 patients per dose cohort. Depending on the BLRM, additional patients may be enrolled in some dose cohorts. The first two patients of each dose level will be enrolled in a staggered approach with at least 1 day apart between first dosing of these patients. Subsequent patients may be enrolled concurrently, with at least 1 day apart from the second patient, whereby a dose cohort must be completed with regards to the DLT assessment period and be reviewed by the Cohort Review Committee (CRC) established for this study before further patients are dosed in the next dose cohort. The BLRM will be assessed for those patients satisfying the requirements for inclusion in the dose-determining set (DDS). After completion of a given dose cohort, or at any time the BLRM is updated, the decision to dose escalate and the actual dose and schedule chosen will depend on the recommendation of the BLRM about the highest admissible dose according to the EWOC principle and medical review of available clinical, pharmacokinetic and laboratory data. The outcome of these analyses and the respective datasets will be reviewed by the CRC consisting of the Investigators, Sponsor and CRO representatives, and independent functional experts as required. The CRC will make the decision to determine the next dose level and schedule for the next dose cohort.

Any dose level cohort that has been declared safe after the DLT period, may be expanded by individual patients in order to collect additional pharmacodynamic (PD) and pharmacokinetic (PK) information to support and/or confirm the mechanism of action and explore doses at the currently tolerated dose level or below. These patients will be counted for the respective cohort at the future CRC meetings and will contribute towards the overall safety, PK, PD and clinical efficacy evaluation.

When the MTD/RP2D is defined, based on the decision of the CRC, approximately 45 additional NOTCH-positive patients with recurrent/metastatic ACC, breast cancer, r/r T-ALL/T-LBL, or any other solid tumour with proven Notch pathway activation will receive the MTD/RP2D dose to

[figure not shown]

ascertain that optimal safety related to efficacy and pharmacodynamics in the tumour and in peripheral blood are achieved.

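### The expansion rule in Protocol 7.4.3 is bounded by the highest unacceptable dose; it should be the lowest

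*Protocol*

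**What the plan says.** Protocol Section 7.4.3, under Estimation of MTD / RP2D, gives a permission to add patients to learn more about safety, tolerability, PK or PD: "Cohorts may be expanded at any dose level below the highest dose deemed unacceptable". The sentence carries no other safety condition.

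Three other places set the limit differently:

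- Later under the same heading, expansion is for "a dose that is considered acceptably safe, i.e., shown to be lower than any potential MTD, may be expanded".
- Protocol 5.1.1 (and the synopsis) requires that the cohort has been declared safe, and gives as one purpose to "explore doses at the currently tolerated dose level or below".
- SAP 2.1.1 repeats that condition: "Any dose level cohort that has been declared safe after the DLT period, may be expanded by individual patients". The SAP does not repeat the 7.4.3 sentence.

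Protocol 10.5.1.2 states the overdose-control rule: a dose with "more than a 25% chance of being in the excessive toxicity category is not considered for the next dose cohort". Excessive toxicity means a true DLT rate of 33% or more.

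**The concern.** The dose-toxicity model has a positive slope, so any dose above an unacceptable one is at least as toxic. The boundary below which expansion is reasonable is therefore the lowest unacceptable dose. Using the highest makes no difference while only one dose has been judged unacceptable. It fails once a de-escalation leads to a second failure, because the lower of the two failed doses lies below the higher one and so qualifies for expansion.

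This is a dosing rule in a first-in-human trial. Read alone, it would allow patients to be added at a dose already judged too toxic. It is not spent. Protocol 2.5.6 says "In parallel, a twice daily schedule of CB-103 is being explored", and 7.4.3 defines the MTD separately for each schedule, so the same sentence governs that escalation.

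**Working it through.** The wording fault needs no arithmetic. The check below asks whether two tested doses can both become unacceptable through steps the protocol permits.

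**Inputs**
- Model (Protocol 10.5.1.3): logit p(d) = log α + β·log(d/150), β > 0.
- Prior (Table 19): equal mixture of two bivariate normals for (log α, log β), means (−1.122, 0.299) and (−1.682, −0.101), SDs (1.98476, 0.9906), correlation −0.0004715777.
- Overdose control (10.5.1.2): a dose is barred if P(overdose) = P(p(d) ≥ 0.33) exceeds 0.25.
- Increments limited in general to 100% (7.4.3).
- Assumption: failing overdose control stands in for 'deemed unacceptable'.

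The posterior is prior × ∏ p(d)^x · (1 − p(d))^(n−x), evaluated on a grid of 1601 × 1201 points.

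**Reproducing the protocol's figures, P(overdose)**

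| Data | Dose | Protocol | Recomputed |
|---|---|---|---|
| Prior (Table 20) | 120 mg | 0.298 | 0.297 |
| Prior (Table 20) | 400 mg | 0.63 | 0.626 |
| Scenario 2 (Appendix 10) | 15 mg | 0.239 | 0.241 |
| Scenario 6 | 30 mg | 0.4 | 0.399 |
| Scenario 6 | 15 mg | 0.206 | 0.198 |
| Scenario 8 | 60 mg | 0.102 | 0.099 |

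The agreement is close enough for this purpose.

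**Path 1: scenario 6 plus one cohort.** "Scenario 6 represents the case that two DLTs are observed in the second cohort in three patients at 30 mg", after 0/3 at 15 mg. The model returns to 15 mg, which is allowed (0.198 < 0.25). Suppose 2 of 3 further patients there have a DLT, giving 2/6 at 15 mg and 2/3 at 30 mg:

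| Dose | P(overdose) | Posterior mean DLT rate |
|---|---|---|
| 10 mg | 0.386 | 0.300 |
| 15 mg | 0.520 | 0.349 |
| 30 mg | 0.759 | 0.447 |

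Both tested doses fail, and both mean rates exceed 33%. Bounded by the highest of the two (30 mg), 15 mg may still be expanded. Bounded by the lowest, it may not. With only 1 of 3 further DLTs at 15 mg, P(overdose) there is 0.247 and the problem does not arise.

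**Path 2: failure higher up.** With no DLT in three patients at each dose before the next step, P(overdose) at the dose to be opened is 0.029 (30 mg), 0.032 (60 mg), 0.089 (120 mg) and 0.148 (180 mg). All are allowed and within the 100% limit; 240 mg would be barred at 0.264. After 2/3 DLTs at 180 mg, P(overdose) is 0.615 there and 0.090 at 120 mg, so de-escalation to 120 mg is allowed. After 2 of 3 further DLTs at 120 mg (2/6):

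| Dose | P(overdose) |
|---|---|
| 60 mg | 0.017 |
| 120 mg | 0.344 |
| 180 mg | 0.821 |

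'Below the highest' admits 120 mg; 'below the lowest' stops at 60 mg. With 1 of 3 further DLTs, P(overdose) at 120 mg is 0.138 and the problem does not arise.

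**The case against.** The sentence is permissive and sits under mandatory rules. Overdose control bars inadmissible doses from the next cohort, the Cohort Review Committee oversees safety and dose decisions, and expansion elsewhere requires a cohort declared safe. Read as a whole, the protocol does not intend expansion at an unacceptable dose. That is right about intent and supports a low impact. It does not make the sentence correct: the overdose rule is worded for the next dose cohort, while this sentence is about adding patients at a dose level to learn more.

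The illustrations have limits. In path 1 even 10 mg fails, so the realistic decision is to stop, not to expand. If only tested doses count as judged, 'below the lowest' would still leave 10 mg open at 0.386; with the stand-in applied to every dose, 10 mg is itself unacceptable and is excluded. In path 2 the mean DLT rate at 120 mg is 0.288, inside the 16–33% target, and the target probability is 0.496, just short of the 50% MTD criterion. Calling 120 mg unacceptable there rests on overdose control alone. These points stand as limits on the examples; the wording fault does not depend on them.

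Nor is there any sign of actual harm. Protocol 2.5.6 reports one DLT, at 600 mg, no MTD reached, and 600 mg once daily declared safe. This too stands.

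**Conclusion.** The sentence is wrong as written. Once two or more doses have been judged unacceptable, it literally permits expansion at all of them except the highest, against three other statements in the protocol and SAP. Two sequences of permitted steps reach that state under the protocol's own prior, with P(overdose) of 0.520 at 15 mg in one and 0.344 at 120 mg in the other.

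The conclusion needs only that DLT risk increases with dose. The figures rest also on treating failure of overdose control as 'unacceptable'; path 1, with both mean rates above 33%, depends on this less than path 2. The paths show that the situation is reachable, not how often it would occur. The figures do not carry over to twice-daily dosing, for which "a separate 2-parameter logistic regression will be used for the assessment of the respective DLT rates"; the wording problem does. Impact is low and no patient effect is shown, but a safety rule in an escalation that is still open should not rely on other sections to correct it.

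**What to change.** In the expansion sentence of Protocol 7.4.3, replace 'highest' with 'lowest'. Setting the limit at or below the highest acceptable dose would serve equally well. The later sentence in 7.4.3, Protocol 5.1.1 and SAP 2.1.1 are sound and need no change. The cost is one word in a protocol amendment, with no new data or analysis and no SAP change.

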### **Phase IIA, Part B - Expansion**

The enrolment into the Part B expansion cohorts for the selected cancer indications will begin after the MTD/RP2D is determined in Part A and reviewed by the CRC. CB-103 will be administered orally at the MTD/RP2D with the dosing schedule being determined in Part A (QD, BID or intermittent).

#### **7.4.4 Dose-Limiting Toxicity (DLT)**

DLT is defined as an adverse event or abnormal laboratory value assessed as unrelated to disease progression, inter-current illness, or concomitant medications, that occurs  $\leq$  28 days following the first dose of CB-103 (Cycle 1) and that meets any of the following criteria shown in the table below. Clinically relevant toxicities will be evaluated according to the National Cancer Institute (NCI)/National Institutes of Health (NIH) CTCAE version 4.03.

For the purpose of dose-escalation decisions, only DLTs occurring during the first cycle of treatment will be necessarily considered in the binary logistic regression model.

Refer to the study synopsis “Dose limiting Toxicity” section for the DLTs criteria.

#### **7.4.5 Dose Modifications, Dose Delays and Treatment Discontinuation**

Every effort should be made to administer CB-103 at the planned dose and schedule. In the event of treatment-related toxicities and DLT with CB-103, dose or schedule adjustments are required and have to be undertaken by the Investigator in the best interest of the patient to continue therapy. In the event of multiple toxicities, the dose modification should be based on the worst toxicity observed (according to the NCI CTCAE, v4.03). Any adjustment to the CB-103 dose should be documented in the eCRF.

Dose adjustments and interruptions criteria are described in the following sections. Depending on the type, severity and timing of the events, the Investigator will determine and decide on dose reductions and resumption of treatment. The following rules have to be followed:

- After Cycle 1 / Day 1, a continuous treatment interruption of more than 14 days will result in discontinuation of the patient from the study. Interruption of treatment not related to CB-103 may not require discontinuation; in such a case treatment continuation must be discussed with the Sponsor.
- Patients with a continuous treatment delay for more than 7 days during cycle 1 in Part A of the study (DLT period) that is not due to a drug-related AE, will be considered non-evaluable for DLT and will need to be replaced accordingly.
- Doses of CB-103 held or missed will not be made up (i.e., cycles will not be prolonged beyond the 28th calendar day in order to make up any missed doses).
- If doses of CB-103 are missed or forgotten to be taken for more than three sequential dosing events and if this happens more than once, this will result in discontinuation of the patient from the study. Dose delays as outlined above to recover from adverse events are allowed.
- If a treatment interruption continues beyond Day 28 of the current cycle, then the day when treatment is restarted will be counted as Day 1 of the next cycle.
- During cycle 1 in Part A (DLT period), any dose adjustments must be discussed with and approved by the Sponsor.
- One dose reduction is allowed per patient. In case the patient shows clinical benefit a 2nd dose reduction might be allowed, but this needs to be agreed upon on a case-by-case basis with the Sponsor. Section [7.4.6.1](#) describes the CB-103 dose modifications for the haematologic and non-haematologic toxicities not clearly attributed to disease.

If a patient concurrently experiences both haematological and non-haematological toxicities, then dose modifications for CB-103 should follow the most conservative approach, as outlined in Section [7.4.6.1.1](#), depending on the specific hematologic and non-hematologic toxicities.

Patients who discontinue from the study for a treatment-related adverse event or an abnormal laboratory value, must be followed up until fully recovered, according to the judgement of the Investigator.

